1.2.2 Pharmacokinetics of NTZ in Humans

NTZ is not detectable in the plasma following oral administration of the drug. The main metabolites of NTZ in humans are tizoxanide and tizoxanide glucuronide. Tizoxanide is highly bound to plasma proteins (>99%). The absorption of NTZ in immediate release tablets is significantly enhanced (C_{max} and AUC of tizoxanide and tizoxanide glucuronide in plasma are more than doubled) when it is administered with food. In fasted human volunteers receiving a single 500 mg dose of ¹⁴C NTZ, approximately one-third of the dose was excreted in urine as tizoxanide and tizoxanide glucuronide, and two-thirds was excreted in feces as tizoxanide. No other significant metabolites were detected. (Investigators Brochure for NTZ 300 mg Tablets, November 2017)

The pharmacokinetics of tizoxanide and tizoxanide glucuronide during repeated oral dosing of nitazoxanide (NTZ) 300 mg extended release tablets administered 600 mg twice daily with food were evaluated in healthy volunteers. Twelve (12) subjects received two NTZ controlled release tablets twice daily with food for 7 days. The pharmacokinetics were studied in plasma up to 12 hours post-dose after the morning dose on Day 1 and Day 7, and before the morning dose on Day 2-6. Based on mixed-effect analysis of variance, the steady state tizoxanide and tizoxanide glucuronide plasma concentrations was reached by Day 2, after one day of

treatment with NTZ at 600 mg b.i.d. The main pharmacokinetics parameters of tizoxanide and tizoxanide glucuronide are summarized in the table below:

Summary of Tizoxanide and Tizoxanide Glucuronide Pharmacokinetics Parameters

PK Parameter (unit)	Tizoxanide		Tizoxanide Glucuronide	
	Day 1 N=12	Day 7 N=12	Day 1 N=12	Day 7 N=12
C _{max} (µg/mL)	5.23 ± 2.71	8.16 ± 4.16	4.88 ± 1.72	8.96 ± 3.48
t _{max} (h)	6.00 (4.00-9.00)	5.00 (3.00-8.00)	6.00 (5.00-11.00)	5.50 (0.00-7.02)
t _{lag} (h)	0.00 (0.00-2.00)	0.00 (0.00-0.00)	0.50 (0.00-2.00)	0.00 (0.00-0.00)
AUC _{0-t} (µg.h/mL)	26.9 ± 16.1	52.5 ± 33.7	29.5 ± 12.1	75.0 ± 37.8
AUC _{0-T} (µg h/mL)	28.6 ± 16.3 ^a	48.3 ± 31.9 ^b	30.5 ± 12.2 ^c	75.2 ± 37.9
C _T (µg/mL)	0.709 ± 0.987	1.72 ± 2.04	1.39 ± 0.846	3.89 ± 2.88
AUC _{0-∞} (µg h/mL)	27.8 ± 17.8 ^b	52.3 ± 35.6 ^b	35.3 ± 16.5 ^d	62.1 ± 24.2 ^e
t _{1/2} (h)	1.66 ± 0.408 ^b	2.19 ± 0.485 ^b	2.70 ± 0.848 ^c	4.99 ± 5.20
λ _z (1/h)	0.441 ± 0.106 ^b	0.331 ± 0.0733 ^b	0.282 ± 0.0902 ^c	0.201 ± 0.0813
C _{avg} (µg/mL)	NA	4.02 ± 2.66 ^b	NA	6.27 ± 3.16

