5.5 Day 2 and 3 Evaluations

A study physician, nurse or other study personnel will visit each subject at home (or at the clinic or another location as agreed with the subject) on each of days 2 and 3 to (i) collect two nasopharyngeal swabs for detecting (RT-PCR) and quantifying (TCID_{50}) influenza virus, and (ii) review symptoms and screen for influenza-related complications including sinusitis, otitis, bronchitis, pneumonia, central nervous system disease and worsening of pre-existing health conditions as well as adverse events. Subjects will be referred for immediate care as needed based on the screening. All information gained from these visits will be included in the case report forms for each subject. In addition, a blood sample for pharmacokinetics will be collected on day 3. The day 2 and day 3 visits will occur at approximately the same time of day that the patient took his/her first dose of study medication (approximately 24 and 48 hours after the first dose). On day 3, the blood sample for pharmacokinetics will be collected before the first dose of that day.

Study sites or subjects may opt out of these day 2 and day 3 visits due to site staffing, patient availability or other practical considerations or preferences; nevertheless at least 75% of subjects enrolled in the trial are expected to complete the day 2 and day 3 visits and related procedures (for viral kinetics and pharmacokinetics).

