10 ADVERSE EVENTS

The term “adverse event” is defined for purposes of this study as any unwanted physical, psychological or behavioral change experienced by a subject during the course of the study and after taking the first dose of study medication regardless of its severity or relation to the study. Adverse events may include symptoms, signs, unexpected worsening of pre-existing conditions, clinically significant changes in laboratory values, diseases and syndromes, and significant and unexpected failures of pharmacological action of other medications. Symptoms of influenza (i.e., those captured in the FLU-PRO Questionnaire) and complications of influenza (e.g., pneumonia, otitis media, bronchitis, sinusitis) shall not be reported as adverse events unless

there is a causal relationship between the study medication and the event. These symptoms and complications will be analyzed separately from adverse events as they are study endpoints.

Bacterial pneumonia, acute bacterial otitis media and acute bacterial sinusitis will be reported as complications of influenza only if the following criteria are satisfied:

Bacterial pneumonia:

1. At least two of the following symptoms: difficulty breathing, cough, production of purulent sputum, chest pain
2. At least two of the following vital sign abnormalities: fever, hypotension, tachycardia, tachypnea
3. At least one of the following findings: hypoxemia, clinical evidence of pulmonary consolidation, elevated white blood cell count or leukopenia
4. Chest radiograph findings of new infiltrates in a lobar or multilobar distribution.
5. Microbiologic criteria: appropriate sputum specimen with fewer than 10 squamous epithelial cells and more than 25 polymorphonuclear cells per low power field

Acute bacterial otitis media:

1. Symptoms of ear pain or earache, ear fullness or decreased hearing
2. One or more of the following otoscopic findings performed by a clinician experienced in otoscopy:
 - Bulging or fullness of the tympanic membrane (convexity of the plane of the eardrum), with loss of anatomic landmarks on visualization,
 - Opacification of the tympanic membrane regardless of color,
 - Erythema of the tympanic membrane, or

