9.1.5 Prior and Concomitant Medication

The prior and concomitant medication tables will summarize the number and percentage of subjects receiving each medication by Level 4 Anatomical Therapeutic Chemical (ATC) classification and standardized medical name.

Analysis Population(s):	All Treated Confirmed Influenza
Derived Variables:	
 • Prior medication classification = medications with stop dates prior to screening date • Concomitant medication classification = medications with administration occurring on or after the date of the first administration of study drug until the end of the study

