10.6.2 Population Pharmacokinetics Analysis

Variables Used for the Analysis

The analysis will require the following variables:

Variable	Source	Format/Notes
Day 3 tizoxanide (T) and tizoxanide glucuronide (TG) values	Laboratory data	
Demographic data	CRF	
Concomitant medications use	CRF	
Adverse events	CRF	

Analysis

Plasma concentrations of T and TG will be summarized descriptively for both treatment groups. Exploratory analyses will be conducted to evaluate relationships between plasma concentrations and age, race, gender, body weight, body mass index, concomitant medications (yes/no), changes in viral titer over time, Time to Symptom Response, and adverse events (yes/no). For continuous factors, the relationship with plasma concentrations will be assessed by Spearman’s correlation analysis and Pearson’s correlation analysis. For categorical factors, plasma concentrations will be compared among groups using the Kruskal-Wallis test.

Analysis Population(s):	Confirmed Influenza, NTZ-treated only
Derived Variables:	
 • Concomitant medications use: if any concomitant medication is used, then “yes”, otherwise “no” • Adverse events: if any adverse event is reported, then “yes”, otherwise “no” • Changes in viral titer over time: see section 10.5.5 • Time to Symptom Response: see section 10.2

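### The Day 3 concentration is compared by any concomitant medication, with no time limit, so medication first taken after the sample counts as a factor for a concentration it cannot have affected

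*SAP*

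**What the plan says.** SAP 10.6.2 takes as its concentration data "Day 3 tizoxanide (T) and tizoxanide glucuronide (TG) values", in NTZ-treated subjects with confirmed influenza. The sample is a single trough. Protocol 5.5 states: "On day 3, the blood sample for pharmacokinetics will be collected before the first dose of that day", at a visit roughly 48 hours after first dose. Protocol 8.4.3 describes the same analysis, calls it exploratory, and adds no time window.

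Two of the factors examined are yes/no variables. For medication the rule is "if any concomitant medication is used, then" yes, otherwise no. For adverse events it is "if any adverse event is reported, then" yes, otherwise no. The test is given as: "For categorical factors, plasma concentrations will be compared among groups using the Kruskal-Wallis test". The yes/no variable is thus the grouping factor and the concentration is the response.

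SAP 10.6.2 sets no window for medication. The SAP's only definition of the term is in 9.1.5: "medications with administration occurring on or after the date of the first administration of study drug until the end of the study". For adverse events, Protocol section 10 covers changes experienced "during the course of the study and after taking the first dose of study medication".

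**The concern.** The medication comparison can only be asking whether co-medication alters exposure. A medicine can alter a concentration only if it was taken before the blood was drawn. Under the rule as written, a subject who takes nothing until Day 10 is grouped with subjects who were co-medicated when the sample was taken. That is a misclassification produced by following the rule, not merely a detail left open.

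What is at stake is how the result reads. Relating pharmacokinetics to response is a stated objective (Protocol section 2), and Protocol 8.4.3 names concomitant medications among the factors. If the yes group contains many later-only users, a finding of no difference could not be taken as evidence that co-medication leaves exposure unchanged.

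**Working it through.** The plan gives no sample size, power or expected usage for this analysis, so there is no figure of its own to reproduce. The check compares definitions and then works out what the mismatch does.

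**Timing**

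- Sample: pre-dose on Day 3, about 48 h (Protocol 5.5, 8.4.3).
- Medication window: first dose to study end (SAP 9.1.5), with the last visit at Day 22, plus up to 3 days.
- Nothing in SAP 10.6.2 or Protocol 8.4.3 limits the variable to the time before the sample.

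**Effect on the comparison**

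Let *a* be the share of subjects exposed before the sample and *y* the share exposed by study end, so that *w = a/y* is the fraction of the yes group truly exposed. Let Δ be the true mean difference between pre-sample users and never-users, and *d* the mean difference between later-only users and never-users. The no group contains never-users only, so the expected observed difference is

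*w*Δ + (1 − *w*)*d*.

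If later-only users resemble never-users, *d* = 0 and the observed difference is *w*Δ.

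The planned test is rank-based, but the factor carries over. Let θ be the probability that a pre-sample user's concentration exceeds a never-user's. If later-only users have the same distribution as never-users, the yes-versus-no probability is *w*θ + (1 − *w*)/2. Its distance from one half is *w*(θ − 1/2).

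**Illustration (assumed rates), y = 60%**

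| Exposed before sample | a/y | Effect remaining |
|---|---|---|
| 15% | 0.15/0.60 | 25% |
| 30% | 0.30/0.60 | 50% |
| 45% | 0.45/0.60 | 75% |

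Over a wider assumed grid (10% to 50% exposed before the sample, and 10% to 40% of the remainder starting only later), pre-sample users make up between 0.10/0.46 = 22% and 0.50/0.55 = 91% of the yes group.

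**What this could mean for power (assumptions throughout)**

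Take 300 × 75% = 225 NTZ subjects with a sample, from the planned group size and the expected Day 2 and 3 attendance. Assume 20% are exposed before the sample, Δ = 0.5 SD and *d* = 0. Use a normal approximation in place of Kruskal-Wallis, with unit SD in both groups, two-sided 0.05: power ≈ Φ(shift/SE − 1.96), where SE = √(1/n_yes + 1/n_no).

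| Coding | Yes / no | Shift (SD) | SE | Power |
|---|---|---|---|---|
| Pre-sample use only | 45 / 180 | 0.50 | 0.167 | 85% |
| SAP rule, 10% of the rest start later | 63 / 162 | 0.36 | 0.148 | 67% |
| SAP rule, 20% of the rest start later | 81 / 144 | 0.28 | 0.139 | 52% |
| SAP rule, 40% of the rest start later | 117 / 108 | 0.19 | 0.133 | 30% |

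In this illustration the smaller, correctly timed yes group has the higher power.

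**Direction**

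Dilution toward no difference depends on *d* = 0. Later medication can mark a poorer clinical course. If exposure relates to course, which the same SAP section examines, then *d* is not zero. With Δ = 0, the observed difference would be (1 − *w*)*d*, a difference not caused by co-medication.

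**The case against.** Several points on the other side have force.

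- **The window is inferred.** SAP 10.6.2 does not itself say up to study end. The phrase comes from a derived-variable note for the summary tables in 9.1.5. Section 10.6.2 does not refer to that note, although it refers to 10.5.5 and 10.2 for other variables. This stands as a description, but it does not rescue the rule: any use counts, without limit, and 9.1.5 is the only definition the SAP offers.
- **Calendar time is not usage.** A reader might infer that, because (504 − 48)/504 = 90% of a 21-day follow-up lies after the sample, most of the yes group is misclassified. The documents do not support that. Protocol 9.6 permits acetaminophen for fever, disallows most other symptom relief, and has medicines for pre-existing conditions continue. This points to early or continuing use, which would precede the sample. What matters is the share of subjects who start only afterwards, and no figure is given.
- **Adverse events are different.** A reader might infer the same fault in the adverse-event variable. An event after the sample can be a legitimate outcome of exposure. Dosing runs for 5 days, and Protocol 1.2.2 reports steady state by Day 2, so a Day 3 trough can stand for the remaining doses. Only events long after the last dose are arguable, and there the documents show no more than an unstated window.
- **Pooling limits the analysis anyway.** One yes/no for all medicines can hardly identify a drug-specific interaction even with the right window. That stands: correcting the window makes the grouping valid in time but does not make the analysis drug-specific.
- **Little depends on it.** The analysis is exploratory and outside the hierarchy in SAP 10.4. The planned listings of medication dates and plasma results would allow a date-restricted rerun. This sets the priority but does not make the rule right.

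**Conclusion.** The point holds for concomitant medication. As written, the rule classifies subjects by medication that may have been first taken after the only concentration was measured.

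If later-only users resemble never-users, the comparison keeps only the fraction *a/y* of its true size. The documents give no usage rates, so the size is unknown. The 25% to 75% range and the power figures are illustrations under assumed rates. Without that resemblance, the bias could go in either direction.

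The documents do not support extending this to adverse events after the sample, or saying that a real interaction would necessarily be missed. The consequence is confined to one exploratory analysis. No primary or secondary conclusion is affected, and the priority is low.

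**What to change.** In SAP 10.6.2, code concomitant medication yes only if it was ongoing at first dose or was taken between first dose and the Day 3 sample. Where the time of intake is missing, use a date cut-off: count the intake only if it falls before the Day 3 visit date, so that the ordering does not rest on the imputed dosing times in SAP 8.4. No change to the adverse-event variable is needed on this ground.

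The cost is a sentence or two of SAP text and minor programming. Protocol 5.10 has the diary capture time of ingestion, and SAP Table 4 lists medication start and stop dates. Three practical limits apply. Table 4 carries no intake times, the plasma listing in SAP Table 6 shows the visit date but not the sampling time, and SAP 8.4 leaves completely missing start dates unimputed, so the handling of those records should be stated. The statistical downside is a smaller yes group. SAP version 1.2, dated TBD in the revision history, already revises the handling of concomitant-medication end dates and dosing times, so the change fits there, before database lock.

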10.7 Efficacy Listings

Efficacy listings will include data specified in Table 5 for all subjects presented by subject number and treatment group.

Table 5. Data Presented in Efficacy Listings

Listing	Data Presented
Time to Symptom Response	Date/time of first dose Date/time of Symptom Response Event time (hours) Censored time (hours)
Time to Ability to Perform All Normal Activities	Date/time of first dose Date/time of Ability to Perform All Normal Activities Event time (hours) Censored time (hours)
Complications of Influenza	MedDRA SOC MedDRA preferred term Reported term Onset date End date Severity Outcome Change in study drug dosage Treatment required
Time to Modified Symptom Response	Date/time of first dose Date/time of Modified Symptom Response Event time (hours) Censored time (hours)
Time to Individual Symptom Response	Date/time of first dose Date/time of Individual Symptom Response Event time (hours) Censored time (hours)
Time to FLU-PRO Domain Response	Date/time of first dose Date/time of FLU-PRO Domain Response Event time (hours) Censored time (hours)
Time to Resolution of Acute Febrile Illness	Date/time of first dose Date/time of Resolution of Acute Febrile Illness Event time (hours) Censored time (hours)
Time to Return to Usual Health	Date/time of first dose Date/time of Return to Usual Health Event time (hours) Censored time (hours)
Virology Data	Study day RT-PCR result Traditional Culture result TCID ₅₀ result
Influenza Antibody Titer Data	Study day Influenza type Antibody titer

11. SAFETY

11.1 Safety Tables and Figures

Unless otherwise specified, all safety tables will be based on the All Treated population and present data by treatment group.

Adverse events summary tables will use the following algorithms for counting subject events:

- Preferred term: Each subject will be counted once within each unique preferred term at the maximum grade.
- System organ class: Each subject is counted only once at the maximum grade at each system organ class level.
- Any event: Each subject with an event is counted only once at the maximum grade.

11.1.1 Summary of All Treatment Emergent Adverse Events (TEAEs)

The summary of all TEAEs will summarize the following:

- The total number of TEAEs;
- The number and percentage of subjects with at least one TEAE;
- The number and percentage of subjects with at least one SAE;
- The number and percentage of subjects with a TEAE by the maximum severity grade; and
- The number and percentage of subjects with a TEAE by the closest relationship to the study drug.

11.1.2 Summaries of TEAEs by SOC and Preferred Term

The number and percent of subjects with TEAEs will be summarized by SOC and preferred term with the following variations in presentation:

- Number and percent of subjects with TEAEs will be summarized by SOC and preferred term;
- Number and percent of subjects with TEAEs will be summarized by SOC, preferred term and severity;
- Number and percent of subjects with grade ≥ 3 TEAEs by SOC and preferred term;
- Number and percent of subjects with TEAEs by SOC, preferred term and relationship to study medication;
- Number and percent of subjects with unexpected TEAEs by SOC and preferred term;
- Number and percent of subjects with SAEs by SOC and preferred term; and
- Number and percent of TEAEs leading to study withdrawal by SOC and preferred term.

11.1.3 Laboratory Results and Changes from Baseline

Numerical hematology and serum biochemistry values will be converted to SI units and classified as Normal, Grade 1, Grade 2, Grade 3 or Grade 4 according to reference ranges indicated in the protocol toxicity grading scale tables (see Appendix II). Urinalysis results will be classified as Normal or Abnormal based on reference ranges provided by the central laboratory.

Hematology, serum biochemistry, and urinalysis laboratory results and change from Baseline will be summarized using descriptive statistics for each visit.

Shift tables will display shifts from Baseline in laboratory results classification (Grade 1/2/3/4 or Normal/Abnormal) by study day.

11.1.4 Summaries of Vital Signs Results and Changes from Baseline

Vital signs data will be classified as Normal, Grade 1, Grade 2, Grade 3 or Grade 4 based on the reference ranges indicated in the protocol toxicity grading scale tables (see Appendix II).

Vital signs results and change from Baseline will be summarized using descriptive statistics for each visit.

Shift tables will display shifts from Baseline in vital signs classification (Grade 1/2/3/4) by study day.

11.1.5 Summaries of Physical Examination Results and Changes from Baseline

The number and percent of subjects with abnormal physical examination findings will be summarized by body system for each visit.

A shift table will display changes in physical examination classification (Normal/Abnormal) at each visit by body system.

11.2 Safety Listings

Safety listings will include data specified in Table 6 for all subjects presented by subject number and treatment group.

Table 6. Data Presented in Safety Listings

Listing	Data Presented
Adverse Events	MedDRA SOC MedDRA preferred term Reported term Onset date End date Severity Serious (Y/N) Relation to study drug Outcome Change in study drug dosage Treatment required
Hematology Laboratory Results Serum Biochemistry Laboratory Results Urinalysis Laboratory Results	Visit Date of visit Laboratory test Result Result units Lower limit of normal Upper limit of normal Classification (L/N/H)
Plasma Tizoxanide and Tizoxanide Glucuronide Results	Visit Date of visit Tizoxanide concentration (µg/mL) Tizoxanide glucuronide concentration (µg/mL)

Listing	Data Presented
Vital Signs Data	Visit Date of visit Weight (kg) Systolic blood pressure (mmHg) Diastolic blood pressure (mmHg) Pulse (bpm) Respiratory rate (bpm) Oral temperature (°F)
Physical Examination Data	Visit Date of visit Body system Result (Normal/Abnormal/Not Done) Abnormality

Appendix I: Schedule of Assessments

	Screening (Day 1)	Baseline (Day 1)	Days 2-22	Days 2-5	Days 2,3	Day 7 ±1	Day 22+3	Unscheduled visit
Signed informed consent	X							
Complete medical history	X							
Physical examination/weight/vital signs	X					X ¹	X ¹	X
Demographics/smoking history	X							
Urine pregnancy test	X							
Record oral temperature	X					X	X	X
Record symptoms and time of onset	X							
Evaluate according to inclusion/exclusion criteria	X							
Collect nasopharyngeal swabs		X			X ²	X	X ³	X
Blood sample for pharmacokinetics					X ⁴			
Blood sample for anti-influenza antibodies		X					X	
Blood sample for laboratory safety tests ⁵		X				X		X
Urine sample for routine urinalysis ⁵		X				X		X
Record concomitant medications		X				X	X	X
Complete baseline symptoms in diary and dispense diary		X						
Randomization/dispense study medication		X						
First dose in office and enter in diary		X						
Instructions re: dosing, concomitant medications, patient diary, birth control, follow-up visits and seeking emergency care		X		X		X		X
Review/record adverse events		X		X	X	X	X	X
Review electronic patient diary entries			X ⁶					X ⁶
Screen for influenza-related complications				X	X			
Review compliance with study medication, collect container with unused medication, complete pill count log form					X	X		X ⁷

¹ Day 7 and 22 physical exam is a brief physical exam (vital signs and nursing physical assessment) including symptom directed physician physical examination as required by patient symptoms. Vital signs include blood pressure, pulse, respiratory rate and oral temperature.

² Nasopharyngeal swabs on days 2 and 3 will be collected at the patient’s home (or clinic or another location as agreed with the patient).

³ Nasopharyngeal swabs collected on day 22 will only be tested for the presence of virus if the sample from day 7 had detectable virus.

⁴ Blood sample collected pre-dose on day 3.

⁵ Laboratory safety tests include hemoglobin, hematocrit, complete blood count (total and differential), platelet count, random blood sugar, total cholesterol, HDL, LDL, triglycerides, albumin, AST, ALT, GGT, alkaline phosphatase, bilirubin (total/direct), BUN, creatinine, sodium, potassium, chloride and routine urinalysis (glucose, proteins and blood).

⁶ All subjects will maintain an electronic diary until day 22 (+3). Site staff will contact subjects as needed during study to ensure timely completion of electronic diary.

⁷ Collection of unused IMP and completion of pill count log form will be performed at unscheduled visit if applicable.

